#### 8.3.2. Outcome definitions

**Table 1.** Regimen discontinuation: Reasons for discontinuation as tabulated below will be collected for all participants switching off CAB+RPV LA regimen.

Code	Reason for Stopping Treatment
1	Treatment failure (i.e. virological, immunological, and/or clinical failure
1.1	Virological failure
1.2	Partial virological failure (multiple blips, low level viraemia)
1.3	Immunological failure - CD4 drop (25% or more)
1.4	Clinical progression
1.5	Resistance (based on test result)
2	Abnormal fat redistribution
3	Concern of cardiovascular disease
3.1	Dyslipidaemia
3.2	Cardiovascular disease
3.3	Weight gain
4	Hypersensitivity reaction (skin eruption etc.)
5	Toxicity, predominantly from abdomen/G-I tract
5.1	Toxicity - Liver
5.2	Toxicity - Pancreas
6	Toxicity, predominantly from nervous system
6.1	Toxicity - peripheral neuropathy
6.2	Toxicity - neuropsychiatric

6.3	Toxicity - headache
7	Toxicity, predominantly from kidneys
8	Toxicity, predominantly from endocrine system
8.1	Diabetes
9	Haematological toxicity (anemia etc.)
10	Hyperlactataemia/lactic acidosis
11	Bone toxicity
12	Social contra-indication
13	Contra-indication unspecified
14	Pregnancy - toxicity concerns (during pregnancy)
15	Pregnancy - switch to a more appropriate regimen for PMTCT
16	Death
17	Toxicity, unspecified
	Availability of more effective treatment (not specifically failure or side effect
18	related)
18.1	Simplified treatment available
18.2	Treatment too complex
19	Drug interaction
19.1	Drug interaction - commencing TB/BCG treatment
20	Injection fatigue (not related to safety)
21	Injection Site Reaction
22	Non-adherence
23	Drug not available
24	Other causes, not specified above
25	Lost to follow-up
26	Defaulter
27	Individual's wish/decision, not specified above
28	Physician decision to discontinue due to confirmed low level viremia (50-200)
29	Physician's decision, not specified above
99	Unknown

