#### **2.** Clinical effectiveness: assessed using the following measures:

- 1. Proportion of individuals, virologically suppressed/undetectable (<50 copies/mL) at 6,12 and 24 months following initiation of CAB+RPV LA regimen
- 2. Proportion of individuals with VL of  $<\!200$  copies/mL at 6,12 and 24 months following initiation of CAB+RPV LA regimen
- 3. Proportion of individuals with confirmed virologic failure (CVF) during the first 6 months, and at 6,12 and 24 months following initiation of CAB+RPV LA regimen defined as

- Two consecutive HIV RNA VL levels ≥200 copies/mL or
- One HIV RNA VL level \ge 200 copies/mL and regimen discontinuation within 4 months of VL \ge 200 copies/mL
- **3.** Resistance Testing: This is a non-interventional study aiming to capture SoC for PLWH in real world setting. Testing for resistance and subtype at virologic failure is part of SoC and the study will include only the clinical sites that follow the guidance for resistance testing.
  - Resistance testing along with subtype will be done for all participants with virologic failure during the 24 month follow-up period while on CAB+RPV LA
  - Resistance testing along with subtype will also be done during the 48 months following any switch from CAB+RPV LA in all participants with subsequent virologic failure on their new regimen(s) during the follow up period

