# AIM 3. Assess the clinical effectiveness among PLWH who initiate CAB+RPV LA regimen

Given that this study involves PLWH in routine clinical care, and who may not attend clinic appointments at 6, 12 or 24 months, a window of 12 weeks around the date in question will be used for virologic failure. Thus, the proportion with virologic failure during first six months, at 6, 12 or 24 months  $\pm$  6 weeks will be used; and if none is available, the first measurement during first six months, after 6, 12 or 24 months (and at most 6 weeks after the measurement).

Proportion of participants who continue to be suppressed (VL of <50 copies/mL) at each time point (after 6, 12 and 24 months of follow up) will be estimated, as well as proportion of individuals with VL of <200 copies/mL. CD4 counts will also be assessed. The proportion of participants with virologic failure (2 consecutive HIV RNA VL  $\geq$ 200 copies/mL or one HIV RNA VL level  $\geq$ 200 copies/mL followed by a discontinuation of CAB+RPV LA regimen) will be estimated and time to failure will be assessed by the Kaplan-Meier method. The two-sided 95% associated confidence interval will be calculated with Kalbfleisch and Prentice's formula. Time to event will be defined as the time between the date of the initiation of CAB+RPV LA regimen and the date of virologic failure. Follow-up will be censored at the analysis time point, or the date of last study contact, or date of discontinuation of CAB+RPV LA regimen, or the date of lost to follow-up, whichever will occur first.

Genotypic resistance testing will be performed in participants with confirmed HIV RNA VL  $\geq$ 200 copies/mL. Resistance interpretation will be given using the Stanford algorithm (https://hivdb.stanford.edu/hivdb/by-mutations). All drug resistance mutations identified will be described and number and percentage indicated. The proportion of participants with genotypic resistance viruses among those with virological failure will be estimated by the number of participants with genotypic resistance viruses divided by the total number of participants with virological failure. The associated two-sided 95% exact (Clopper–Pearson) confidence intervals will be calculated. The frequency of viral subtype among those with virologic failure will be reported.

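### AIM 3 censors time to virologic failure at any regimen stop, including stops made because of viraemia below 200 copies/mL, so the Kaplan-Meier estimate leans low as a measure of failure after initiation

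*Protocol*

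**What the plan says.** Section 8.3.2 defines confirmed virologic failure by two limbs. The first is "Two consecutive HIV RNA VL levels ≥200 copies/mL or" the second, which is one level of at least 200 "and regimen discontinuation within 4 months of VL" at or above 200. AIM 3 in section 8.7 repeats both limbs, without the four-month limit on the second. Either way, at least one result of 200 copies/mL or more is required.

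For the analysis, AIM 3 says that the proportion with failure "will be estimated and time to failure will be assessed by the Kaplan-Meier method". Censoring is at the analysis time point, the last study contact, "or date of discontinuation of CAB+RPV LA regimen, or the date of lost to follow-up, whichever will occur first". The rule draws no distinction by reason for stopping.

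Table 1 in section 8.3.2 lists three reasons for stopping that can apply without a result of 200 or more:

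- code 1.2: "Partial virological failure (multiple blips, low level viraemia"
- code 28: "Physician decision to discontinue due to confirmed low level viremia (50-200"
- code 1.5: "Resistance (based on test result"

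Under AIM 2, reasons for stopping and the number of people with blips from 50 to below 200 copies/mL are tabulated. Neither enters the AIM 3 estimate. The one sensitivity analysis described in section 8.7 is multiple imputation of missing parameters.

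**The concern.** Kaplan-Meier is unbiased for failure risk when those censored at a given time have the same later risk as those who remain under observation. Take a participant with results of 120 and then 160 copies/mL whose physician stops the regimen and records code 28. No event can be recorded. Follow-up ends on the stop date, and the method gives this person the later hazard of those still on the regimen. The stop was made because of the viral load, so this is where the assumption is least credible.

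Objective 3 in section 7 asks for the proportion with virologic failure at 6, 12 and 24 months after initiation, among people who initiate. It is not limited to time on the regimen, and AIM 3 does not label its result that way. The trial used as the sizing benchmark in section 8.4 is described there as defining failure by two confirmed results of 50 or more. Confirmed viraemia of 50-199 is therefore failure in the benchmark but can only lead to censoring here. At stake is a downward lean in one of the study's effectiveness measures.

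**Working it through.** **Inputs from section 8.4.** N = 1000; failure 2-6% (20-60 people); discontinuation 8-16% (80-160 people); stated precision for failure 0.9-1.5 points.

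**Inputs not in the protocol (assumed).** Share of discontinuations that are virologically driven with no result of 200 or more: 5-10%. Probability that such a person would have failed by month 24 if kept on the regimen: 25-50%, with 100% as the limit.

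**Step 1: the plan's own figures.** Exact Clopper-Pearson limits are 0.0123-0.0307 for 20/1000 (half-width 0.92 points) and 0.0461-0.0766 for 60/1000 (1.52 points). These match Table 2.

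**Step 2: people affected.** 80 × 0.05 = 4; 160 × 0.10 = 16. So 4-16 per 1000 are censored because of their viral load.

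**Step 3: understatement against a no-switching quantity, by direct count.** 4 × 0.25 = 1 per 1000 (0.1 point); 16 × 0.50 = 8 per 1000 (0.8 point).

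**Step 4: every such stop counted as an event.**

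| Failure under the definition | plus 4 | plus 16 |
|---|---|---|
| 20/1000 = 2.0% | 24/1000 = 2.4% | 36/1000 = 3.6% |
| 60/1000 = 6.0% | 64/1000 = 6.4% | 76/1000 = 7.6% |

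The shift is 0.4 to 1.6 points.

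**Step 5: check on the Kaplan-Meier scale.** With event share p and censored-discontinuation share d, both uniform over 24 months, the estimate is 1 − (1 − p − d)^(p/(p + d)).

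- Protocol rule, p = 0.02, d = 0.16: 1 − 0.82^(0.02/0.18) = 2.18%. This is slightly above the crude 2.0%.
- Composite, 16 stops moved from d to p: 1 − 0.82^(0.036/0.18) = 3.89%, a shift of 1.7 points.
- Those 16 kept on the regimen, half failing at times uniform over their remaining follow-up (numerical integration): 3.06%, a shift of 0.9 point.
- Low end (p = 0.02, d = 0.08, 4 stops, 25% failing): a shift of 0.1 point.

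The direct counts in steps 3 and 4 therefore hold to within about 0.1 point.

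**Step 6: wider assumption.** If 20% of 160 discontinuations were of this kind (32 people) and half would have failed, simulation on the Kaplan-Meier scale gives about 1.7 points. The size depends mainly on a share that the protocol does not state.

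**The case against.** Several stronger readings are tempting, and the protocol does not support them.

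- **That these participants are counted as non-failures.** Kaplan-Meier removes them from the risk set and gives them the hazard of those remaining. Its estimate lies a little above the crude on-regimen proportion (2.1-2.2% against 2.0%). The understatement exists only relative to a no-switching or composite quantity.
- **That the bias exceeds the study's precision.** The 1.6-point figure treats every low-viraemia stop as a failure, which is a change of endpoint. At the same share with 25-50% failing, the effect stays below the 0.9-point half-width, although at the top of that range only just.
- **That documented resistance routinely escapes the endpoint.** AIM 3 ties genotyping to a confirmed result of 200 or more, which is already failure. A code 1.5 stop without such a result should be uncommon. It is not impossible, because the case report form asks for resistance details at discontinuation without a viral-load condition.
- **That sites which switch early will look more effective.** No comparison of sites is planned.

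It can also be said that failure while on the regimen is a legitimate quantity and that sensitivity analyses are often left to the SAP. CVF is only one of three effectiveness measures, next to viral load below 50 and below 200. Reasons for stopping and blips are tabulated, and people who switch are followed for 48 months.

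Much of this stands, and it limits the point. It does not remove it. The protocol itself fixes the censoring rule and the estimator, and leaves the result unlabelled under an objective framed from initiation. The AIM 2 tabulations let a reader see how many such stops occurred, but do not carry them into the estimate. Post-switch outcomes under AIM 4 describe the next regimen.

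**Conclusion.** The point holds for stops coded 1.2 and 28, and for the uncommon code 1.5 stop with no result of 200 or more. Censoring at these stops is informative, and its direction is toward a lower failure estimate.

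On assumed inputs the understatement is probably modest: about 0.1-0.8 points by direct count (up to 0.9 on the Kaplan-Meier scale), and 1.6 points at most if all 16 stops are counted as failures. These figures rest on a 5-10% share and a 25-50% failure probability, neither of which the protocol gives. A larger share would scale the effect up. The half-width of 0.9-1.5 points is a yardstick for size only; it does not allow for this bias. The correction is worthwhile because it is cheap. The document does not show that the effectiveness result is materially wrong.

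**What to change.** In AIM 3:

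1. Keep the definition of confirmed virologic failure.
2. Label the present Kaplan-Meier estimate as failure while on CAB+RPV LA.
3. Co-report at 6, 12 and 24 months a pre-specified sensitivity analysis in which a discontinuation coded 1.1, 1.2, 1.5 or 28 is an event on the discontinuation date and is not censored.
4. Leave out the parent code 1 unless the recorded reason is virological, because it also covers immunological and clinical failure.

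The case report form already collects the discontinuation date and reason code, so no new data are needed. The cost is analysis wording and a co-reported figure that will be somewhat less favourable. No change to clinical management is implied.

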### 7. RESEARCH QUESTION AND OBJECTIVE(S)

Following the initiation of CAB+RPV LA regimen among people living with HIV (PLWH), the study will aim to assess effectiveness, discontinuation, and resistance over 24-months of follow-up period in approximately 1000 participants.

The specific objectives are to:

- 1. Describe study population initiating CAB+RPV LA regimen, by baseline demographic and clinical characteristics
- 2. Assess adherence, durability and discontinuation for PLWH starting CAB+RPV LA regimen
  - Proportion of participants discontinuing the CAB+RPV LA regimen and lost to follow-up will be assessed.
    - Reasons for discontinuation will be assessed.
  - Non adherence to dosing schedule will be assessed by
    - a. Estimating the number of participants that missed one or more consecutive injections without taking daily oral bridging therapy or any other oral ARV regimen while not on CAB+RPV LA regimen and mean and median number of injections missed during a 12-month period
    - b. Estimating the number of participants who received the injections seven or more days later than their scheduled injection visit and median duration of delayed injections
- 3. Assess the clinical effectiveness (i.e. proportion of participants experiencing virologic failure) among PLWH who initiate CAB+RPV LA regimen and had suppressed viral load (VL <50 copies/mL) at regimen initiation
  - Estimate the proportion of participants with virologic failure, during the first 6 months after initiation of CAB+RPV LA regimen
  - Estimate the proportion of participants with virologic failure at 6, 12 and 24 months after initiation of CAB+RPV LA regimen
- 4. Monitor for resistance in case of VF while on CAB+RPV LA or after switching to a subsequent ARV regimen among individuals who switched off CAB+RPV LA regimen for any reason
  - Describe the ARV regimen participants are switched to after discontinuation of CAB+RPV LA regimen
  - Describe virologic outcomes at 12, 24, 36 and 48 months after discontinuation of CAB+RPV LA regimen
  - Monitor for virologic failure and resistance during the 48 months following the switch
    - Resistance test to be done for all participants with virologic failure during the follow-up period

 HIV subtype test to be done for participants with virologic failure during the follow-up period, if subtype data is not available

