#### 8.2.2. Inclusion Criteria

The study population will consist of HIV positive male or female aged 18 years or over from NEAT ID Network clinical sites who are prescribed CAB+RPV LA regimen and:

- Virologically suppressed (HIV-1 RNA <50 copies/mL) at the time of regimen initiation.
- No evidence of prior virological failure with agents of the NNRTI and INI class
- No evidence of present or past documented viral resistance to, agents of the NNRTI and INI class

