## Resistance Testing

Subject ib
Please record all previous HIV drug resistance tests and any historic HIV-1 subtype information where available.
In the event of virological failure while on the CAB+RPV LA Regimen, please record the resistance tesing along with subtype information.
For patients who switch to another regimen, please record all resistance testing, with subtype information, carried out in the event of virological failure in the 48 months following the switch.
Resistance test carried out?  O No O Yes
Date of resistance Is test report testing available? Was new resistance identified?  RESIDENT  Was new resistance Class of ARV Drug  ARV Drug Name - 1 per row List each mutation data available?  RESPEC  RESMUT  HIVSUB  SUBYN  HIVSUB  HIVS

Data Review Reason	Review Date	)	Notes for Next Review
CRREAS	CRDAT		CRNOT

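### Aim 3 divides resistant cases by all virologic failures, so a failure without a genotype result counts as non-resistant, and the protocol disagrees with itself on which failures are tested

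*Protocol*

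**What the plan says.** The Aim 3 text in Protocol section 8.7 sets the estimator as the "number of participants with genotypic resistance viruses divided by the total number of participants with virological failure", with an exact Clopper-Pearson 95% interval.

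On who is genotyped, the protocol makes two kinds of statement:

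- Section 8.7, Aim 3: "Genotypic resistance testing will be performed in participants with confirmed HIV RNA VL" at or above 200 copies/mL.
- Section 7, objective 4: "Resistance test to be done for all participants with virologic failure during the follow-up period".
- Section 8.3.2, third outcome item: "Resistance testing along with subtype will be done for all participants with virologic failure during the 24 month follow-up period while on CAB+RPV LA".
- Section 8.5 admits only sites whose standard of care is to test every participant at failure.

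On what counts as failure, Aim 3 has two routes: two consecutive values at or above 200 copies/mL, or one such value "copies/mL followed by a discontinuation of CAB+RPV LA regimen) will be estimated and time to failure will be assessed by the Kaplan-Meier method". Section 8.3.2 has the same two routes, with a 4-month limit on the second, and gathers both under the label "Proportion of individuals with confirmed virologic failure (CVF) during the first 6 months, and at 6,12 and 24 months".

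Section 8.4 assumes 50% resistance among failures. It takes the number genotyped as 20 to 60, which is every failure at a 2 to 6% failure rate in 1000 participants.

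The Resistance Testing form in Annex 1 has a no/yes item for whether a test was carried out and another for whether its report is available.

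**The concern.** The numerator can only come from participants with a genotype result. The denominator takes every failure, with or without one. A failure without a result therefore cannot add to the numerator but always adds to the denominator, which is the same as recording it as free of resistance.

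Read literally, the Aim 3 text creates such a group itself, because a single elevated value followed by discontinuation is a failure but not a confirmed viral load. Even with the testing rule settled, this is a non-interventional study that extracts medical records. Some failures may have no test or no retrievable report, and Aim 3 gives no rule for them. The formula also departs from the general convention at the start of section 8.7, where percentages rest on the non-missing sample size.

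Resistance at failure is one of the four study objectives, and the error makes resistance look rarer than it is.

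**Working it through.** **Inputs.** True resistance 50% and 20 to 60 failures (section 8.4); exact Clopper-Pearson intervals (sections 8.4 and 8.7). The share of failures with a genotype result is not given anywhere, so it is varied here as an assumption.

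**Reproducing Table 4.** Clopper-Pearson limits at 50%:

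| Failures, all tested | Computed limits | Table 4 |
|---|---|---|
| 20 | 0.272 to 0.728 | 0.27 to 0.73 |
| 30 | 0.313 to 0.687 | 0.31 to 0.69 |
| 40 | 0.338 to 0.662 | 0.34 to 0.66 |
| 50 | 0.355 to 0.645 | 0.36 to 0.64 |
| 60 | 0.368 to 0.632 | 0.37 to 0.63 |

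The limits agree to two decimals. The precision of 21.9% and 12.7% in the section 8.4 text is the normal-approximation half-width, 1.96 × √(0.25/n), for n = 20 and n = 60. The exact half-widths are 22.8% and 13.2%. Table 4 is correct for n participants with a result.

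**Effect of the denominator.** Let F be the number of failures, t the share with a result and p the true resistance proportion, taken as equal in tested and untested failures. Resistant cases found = F × t × p. The Aim 3 formula gives F × t × p / F = t × p. Dividing by the number with a result gives F × t × p / (F × t) = p.

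With p = 50%:

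| Assumed share untested | Aim 3 formula |
|---|---|
| 0% | 50% |
| 10% | 45% |
| 20% | 40% |
| 30% | 35% |
| 40% | 30% |
| 50% | 25% |

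**With intervals, 20% untested.**

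- 60 failures, 48 with a result, 24 resistant: Aim 3 formula 24/60 = 40.0% (27.6 to 53.5); result-based denominator 24/48 = 50.0% (35.2 to 64.8).
- 20 failures, 16 with a result, 8 resistant: 8/20 = 40.0% (19.1 to 63.9), against 8/16 = 50.0% (24.7 to 75.3).

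For 60 failures the Aim 3 interval is also narrower (53.5 − 27.6 = 25.9 points, against 64.8 − 35.2 = 29.6), so it claims precision from participants who supplied no information. With 30% untested, 21/60 = 35% (23.1 to 48.4) no longer covers the true 50%.

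**Bounds without the alikeness assumption.** For 60 failures, 12 of them without a result: if none of the 12 is resistant, 24/60 = 40%; if all are, (24 + 12)/60 = 60%. The Aim 3 formula always reports the lower bound as if it were the estimate.

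**The case against.** The strongest reply is that there may be no untested group. Sections 7, 8.3.2 and 8.5 call for testing at every failure, sites are chosen for that practice, and section 8.3.2 calls both failure routes confirmed, so Aim 3 may mean nothing narrower. The regimen form also asks for resistance details at discontinuation, which covers the single-value route. This stands as a reason not to conclude that single-value failures will go untested. It does not settle the wording: Aim 3 speaks of a confirmed viral load, not a confirmed failure, and section 8.4 uses the same adjective for a repeat measurement when it describes the cited trial.

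A second reply is that the two no/yes items sit on a form that also collects historical tests, so they do not show that the sponsor expects untested failures. That is fair. They show only that the data can hold such a case, for which the stated formula gives the wrong answer. The multiple imputation in section 8.7 is a sensitivity analysis described for parameters that influence the outcome; it does not alter the Aim 3 formula.

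A reader might also infer that the numerator counts resistance of any class or age, because entry requires only "No evidence of present or past documented viral resistance to, agents of the NNRTI and INI class" and leaves other classes open. The protocol does not say so. It is silent on class and emergence, that coding is commonly left to a statistical analysis plan, Aim 3 promises a description of all mutations, and the form records drug class and asks "Was new resistance identified". This is not an error.

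**Conclusion.** The point holds in two parts. First, the Aim 3 testing sentence, read literally, is narrower than sections 7, 8.3.2 and 8.5 and than the basis of Table 4, and these must be reconciled. Second, under either testing rule the stated denominator scores failures without a result as non-resistant and biases the proportion downward.

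The size depends wholly on the share without a result, which the documents do not give. It is zero if every failure has one. At a true 50% it is 10 percentage points for an assumed 20% untested, if tested and untested failures are alike. A reader might take a particular bias as established or Table 4 as wrong. Neither follows: the untested share is an assumption, and Table 4 is right for the number genotyped. The study is descriptive with no hypothesis test, so this is an estimator to correct and a wording conflict to remove, not a threat to the design.

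**What to change.** 1. Reword the Aim 3 testing sentence so that it names the same group as sections 7, 8.3.2 and 8.5, with both failure routes included explicitly.
2. Make the main denominator the failures with an available genotype result, identified from the existing items on test carried out and report available. Because the same form holds historical tests, match the test date to the failure.
3. Report the number of failures without a result, and give best-case and worst-case proportions over all failures.
4. State beside Table 4 that its precision applies to the number genotyped.

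Optionally, report resistance by drug class and as new or pre-existing from the fields already collected.

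This is a change of wording with no new data. A stricter denominator that required particular genome regions to be sequenced would need a new field, since the form has none, and is not asked for here. The price is a somewhat wider interval when some failures lack a result: 29.6 instead of 25.9 points in the 60-failure example.
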